Number of Subjects	Up to 10 subjects who complete
Diagnosis and Main Inclusion Criteria	
• ≥ 21 years of age• Diagnosis of mild to moderate obstructive sleep apnea via a PSG within the last 12 months
Study Product /Indication for Use	BONGO NASAL EPAP Device Intended for adult patients for the treatment of mild to moderate obstructive sleep apnea
Control/Comparator	None

3 Introduction

This document is a protocol for a human research study. This study is to be conducted according to US (21 CFR Part 812) and international standards of Good Clinical Practice (International Conference on Harmonization ICH-E6, ISO 14155 and other applicable government regulations, and Institutional research policies and procedures).

3.1 *Background*

Sleep is a necessary component of good health and comprises about one-third of a human life. The average person sleeps about 3000 hours per year; thus, the importance of sleep should not be underestimated. Adequate quantity and quality of sleep is essential to most psychological and physiological processes. Obstructive sleep apnea (OSA) is a common and serious condition that impairs sleep and can compromise an individual's health.

OSA can be characterized by a periodic full closure or partial obstruction in the upper airway due to neurological and/or anatomical features factors including micro- and retrognathia and impaired neuromodulation to the upper airway. Risk factors also include obesity, male, or post-menopausal females, age, neck size, and upper airway malformations such as deviated septum (Epstein, et al., 2009; Kapur, 2010). The obstruction or upper airways resistance results in cyclical reductions in blood oxygen, increased work of breathing, and arousals (cortical and sympathetic) from sleep. These sequelae may in turn have short- or long-term results such as insulin resistance, type two diabetes, stroke, incident coronary heart disease in men, neurocognitive deficits, and hypertension. Along with damage to health, these conditions may and also have significant negative workplace and economic consequences (Gottlieb et al., 2010; Marin, et al., 2005; Redeker & McEnany, 2011; Redline et al., 2010; Rosekind, et al., 2010; Yaggi, 2005).

Continuous positive airway pressure (CPAP) is the most often frequently prescribed therapy for OSA. CPAP provides a pneumatic splint to the upper airway, thus preventing closure due to critical closing pressure. Other therapeutic options include oral appliances, surgical procedures, and, most recently, expiratory positive airway pressure (EPAP) devices (Provent K071560; K080983; K090398; K102404, Theravent, San Jose).

While CPAP is considered the therapy of choice, adherence to short-term (acclimation) and long-term therapy remains problematic (Somers, Peterson, Sharma & Yaramchuc, 2011). Rates of adherence, defined as usage of at least 4 hours for 70 percent of the nights, are reported to average between 30% and 60%; one study found that 31% of their population did not fill their prescription for CPAP (Sin, Mayer, Man & Pawluk, 2002; Wolkove, Baltzan, Kamel, Dabrusin & Palayew, 2008). Thus there is still an opportunity to improve therapeutic targets for patients with OSA.

Expiratory positive airway pressure (EPAP) is such a therapeutic target. Data support the use of the EPAP for the treatment of OSA. At least two potential mechanisms of action have been suggested. One of these is increased functional residual capacity,

which produces tracheal traction, resulting in lessened propensity for upper airway/pharyngeal collapse. An alternative mechanism is passive dilation of the airway, which reduces flow limitation (Braga, Chen, Burschtin, Rapoport & Ayappa, 2011; Colrain, Brooks & Black, 2008; Heinzer et al., 2008; Owens et al., 2012; Rosenthal, Massie, Dolan, Loomas, Kram & Hart, 2009; Walsh et al., 2011).

The Provent device provides for an “unimpeded flow of air during inhalation, but closes so that exhalation occurs against a fixed orifice” thus creating EPAP (Rosenthal, et al, 2009). The Provent device is comprised of two nasal inserts which are affixed to the nares via adhesive, each containing an actuated valve. Several studies provide the long-term (up to 12 months) effectiveness of Provent versus sham devices in multicenter trial with up to 250 subjects enrolled. These studies demonstrated an effective therapeutic approach in reducing the apnea hypopnea values (Berry et al., 2010;Kryger, et al., 2011). These studies further demonstrated that no serious adverse events occurred over the span of the study.

The BONGO NASAL EPAP device was developed to provide similar principals of operation and is posited to be substantially equivalent to the Provent device. This mechanism provides for minimal inhale resistance and controlled exhale resistance which increases expiratory airway pressure upon exhalation as noted above.

The Bongo differs from the Provent in that it is reusable, does not use adhesive, and seals against the opening of the nares instead of the outer edges of the nares and nose. During product development, bench testing was conducted on the Bongo, including age testing, environmental testing (high temperature, low temperature, and humidity), cycle testing, drop testing, and cleaning testing. Comparative testing against the Provent device was also conducted including inhale resistance testing and exhalation flow rate testing.

3.2 Investigational Product Description

The BONGO NASAL EPAP device consists of two nasal inserts (a connected pair), each containing an actuated valve, with a patient attachment mechanism. The device works by providing an inhalation port that offers minimal inhale resistance during inhalation, but is closed by the actuated valve so that exhalation occurs against a fixed orifice. This mechanism provides increased EPAP upon exhalation.

The design incorporates elements of the currently marketed Nasal-Aire II (K022465). The Nasal-Aire II is a nasal interface that delivers positive pressure from the CPAP machine to the patient. The materials to be used in the investigational product are similar to those in the currently marketed product. Like the Nasal-Aire II, the Bongo will seal against the nares.

Nasal-Aire II

[figure not shown]

Nasal-Aire II in Use

[figure not shown]

Nasal Inserts of Nasal-Aire II

Bongo Renderings

[figure not shown]
Top View

[figure not shown]
Bottom View

[figure not shown]
Front View

Exploded View
(Nasal Inserts in Yellow
Valves in Gray)

Cross-section showing Valve OPEN

Cross-section showing Valve CLOSED

The Bongo is made of silicone and polypropylene. A total of four (4) nasal insert sizes (SM, MD, LG, and XL) will be available during this study. Subjects will fit the most appropriate size for comfort during the first clinic visit. A total of two (2) valves with different resistances (R1 and R2) will be available during this study. Each nasal insert size will have the capability to use each resistor for a total of 8 variations (e.g. Nasal Insert MD will have R1 and R2 options).

4 Study Overview

4.1 Study Objectives

The objective for this study is to provide the data required for inclusion within a pre-market notification (510k) submission. The study design and end points have previously been discussed with the Food and Drug Administration.

4.2 Primary Endpoint

The primary endpoint for the study is change in AHI, defined as the difference in AHI between the diagnostic study and PSG 2 with the Bongo. A reduction in AHI to less than 10 or an AHI reduction by at least 50% from the baseline is considered clinically significant.

5 Study Design and Procedural Detail

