6.1 Screening/Baseline

Subjects will be first phone screened using existing patient rolls at each individual sleep center. Subjects who meet the initial qualifications will be asked to attend an in-clinic visit (Screening Visit).

During this Screening Visit the following will occur:

- Informed Consent Process
- Subjects will be asked to bring their CPAP/APAP machines and/or their data card for downloading and review. The following data from the past 30 days will be downloaded: pressure setting, average hours of use per night, % of time used, and residual AHI. If the subject has no data on their data card over this time period, and/or the subject has been diagnosed and is unable or willing to use CPAP, this will be noted on their record.
- Subjects will fit for the nasal inserts:
 - Subjects will select the size of the BONGO according to Bongo IFU
 - Subjects will be allowed a minimum of 10 minutes of acclimation with the valve R1; ensure that subject has some “supine” time during the acclimation period.
 - Subjects will be asked on a scale of 1-10 where their tolerability level of the device resides (<5, not qualified; ≥5, will qualify to move ahead).
- Once a subject is deemed eligible to participate, baseline measurements including BMI, vital signs, medications, and the above measures will be recorded.

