6.2 PSG Studies

Two in-lab PSG studies will be performed while using the Bongo device. PSG 1 will be performed on a separate visit after the Screening Visit. PSG 2 will be performed after a two week (14 day) period of at home use with the Bongo.

Sites will follow the standard sleep protocol methods that include patient preparation procedures, the standard recording montage, the proper instrument calibration and bio-calibration procedures that must precede the initiation of the collection of the PSGs according to the American Academy of Sleep Medicine (AASM) Manual for Scoring Sleep and Associated Events (2007), a standard PSG montage, recording channel labels and the order to be used will be:

- left electrooculogram (E1/M2)
- right electrooculogram (E2/M1)
- submental electromyogram (chin1/chin2)
- submental electromyogram (chin2/chin3)
- electroencephalogram (C3/M2)
- electroencephalogram (O2/M1)
- electroencephalogram (F4/M1)
- electroencephalogram (C4/M1)
- electrocardiogram (ECG)

- thoracic inductance plethysmography (TEFFORT)
- abdominal inductance plethysmography (AEFFORT)
- nasal/oral nasal air pressure transducer (PFLOW),
- oxygen saturation (SaO₂)
- left anterior tibialis electromyogram (L LEG)
- right anterior tibialis electromyogram (R LEG)

Prior to each PSG, the site will screen the subject for acute alcohol intoxication by obtaining a breath alcohol test or equivalent. If testing shows any evidence of recent alcohol use, then the subject will be sent home after being counseled to refrain from alcohol use and return to the site within one week for the PSG. Subjects will be allowed no more than two attempts to participate if they are intoxicated upon arrival to the sleep clinic.

In addition, prior to each PSG, the site will call the subject to remind them of the upcoming PSG, they will be asked if they have any current cold or nasal condition which would prevent them from attending. At the time of the PSG, the research staff will assess the subject for nasal infection, nasal congestion, or nasal allergies that may impact the ability of the subject to breathe through the nose. If observation shows any evidence of nasal infection, nasal congestion, or nasal allergies, then the subject will be sent home and asked to return to the site after the symptoms have resolved.

[figure not shown]
A standard type pre (PM) sleep questionnaire will also be completed at a PSG visit. This questionnaire will assess the subjects day of test activity.

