To record data during a PSG with the Bongo, a sampling tube connecting the nasal insert to the pressure transducer is used. Each nasal insert has a sampling port for connecting a sampling tube. The sample tubes and instructions for use will be supplied by InnoMed to the site for this purpose.

During PSG 1:

1. Subjects may sleep in the position that is the most comfortable for them.
2. All subjects will begin with the R1 valve in place.
3. Subjects will sleep with the R1 valve until the completion of one REM cycle. Calculate the AHI at this time.
 - a. If the AHI is below 10 (AHI < 10), maintain the R1 valve.
 - b. If the AHI equals or exceeds 10 (AHI ≥ 10), change to the R2 valve for the remainder of PSG 1.
4. Continue to calculate the running AHI of subjects that remained on the R1.
 - a. If the running AHI equals or exceeds 10 (AHI ≥ 10), change to the R2 valve for the remainder of PSG 1.

5. At the end of PSG 1 and prior to the subject leaving the facility:
 - a. Calculate and record the AHI for the overall time the R1 valve was used.
 - b. If applicable, also calculate and record the AHI for the overall time the R2 valve was used. (Note that the AHI for R1 and R2 should not be combined).

Prior to the subject leaving the facility, the research staff will need to score and assess whether the subject qualifies for the at home portion of the study. Score using the AASM 3% and/or arousal criteria.

1. Compare R1 AHI, as well as the R2 AHI (if applicable), to the subject's baseline AHI (from their diagnostic study).
2. If the subject while using the Bongo had an AHI reduction to less than 10 (AHI < 10) or an AHI reduction by at least 50% (AHI reduction $\geq 50\%$) compared to the baseline, then the subject qualifies for the at home portion of the study.
 - a. Send the subject home with either the R1 or R2 valve only, whichever valve the subject had the lowest AHI with.
3. If the subject did not have the AHI reductions described above with either valve, then that subject will be terminated from the remainder of the study.

Subjects that qualify for the at home portion of the study will continue using the Bongo at home for two weeks. Subjects will complete a daily use log while using the Bongo at home.

Enrollment will continue until such time a total of up to 10 subjects have completed all components of the study.

In preparation for the home use portion of the study, the site will:

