6.5 Inclusion Criteria

- Capacity and willingness to sign informed consent
- ≥ 21 years of age
- Diagnosis of mild to moderate OSA (AHI ≥ 5 and AHI ≤ 30) within 12 months of the screening visit with the 3% hypopnea criteria
- Able to tolerate using the device during a day time trial/acclimation
- Are currently using CPAP or have been prescribed CPAP and are considered CPAP non-adherent (as per either their CPAP data card and/or verbal confirmation of a diagnosis and unwillingness to use CPAP)

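### The baseline AHI may be 12 months old at screening, and no criterion or planned check covers surgery, other OSA treatment or weight change since the diagnostic study

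*Combined protocol and SAP*

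**What the plan says.** - **Endpoint.** Section 4.2 makes the primary endpoint the change in AHI, "defined as the difference in AHI between the diagnostic study and PSG 2 with the Bongo".
- **Age of the baseline.** Section 6.5 asks for a diagnosis with "AHI ≥ 5 and AHI ≤ 30) within 12 months of the screening visit". The study summary (section 2) words it as "Diagnosis of mild to moderate obstructive sleep apnea via a PSG within the last 12 months".
- **No new untreated study.** Section 6.2 states: "Two in-lab PSG studies will be performed while using the Bongo device". The PSG 1 result is likewise compared "to the subject's baseline AHI (from their diagnostic study"). The CPAP download in section 6.1 gives residual AHI on CPAP, which is not untreated AHI.
- **No control.** The study summary gives the comparator as none, and section 8 plans descriptive statistics only.
- **What is recorded.** Section 6.1 says: "Once a subject is deemed eligible to participate, baseline measurements including BMI, vital signs, medications, and the above measures will be recorded". The schedule in section 7 places medical history and height/weight at screening, and concomitant medications at screening and at termination.
- **What can move untreated AHI.** Section 3.1 says: "Risk factors also include obesity, male, or post-menopausal females, age, neck size, and upper airway malformations such as deviated septum". It also lists oral appliances and surgery among the treatments for OSA.
- **Eligibility.** Sections 6.5 and 6.6 contain nothing on surgery, non-CPAP OSA treatment or weight change since the diagnostic study. Section 5.4 covers medications only.

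**The concern.** In a single-arm study, the change in AHI can be credited to the device only if untreated AHI was stable between the diagnostic study and PSG 2. Nothing in the plan secures or checks that stability. A subject whose septum was corrected, who had bariatric surgery or who lost much weight after diagnosis meets every criterion as written, and the resulting fall in AHI enters the primary endpoint as Bongo effect. The same holds for a subject who has started an oral appliance and wears it during the PSGs, since nothing addresses that. With 10 completers, one or two such subjects can move the mean visibly, and the planned data would not show whether there were any.

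**Working it through.** The plan's sample size rests on no alpha, power, effect size or SD, so there is no figure of its own to reproduce. The check is a reading of the criteria plus an illustration.

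**1. Age of the baseline at the endpoint.** Up to 12 months at screening, plus the interval from screening to PSG 1 (no limit stated), plus 14 days at home, plus up to 3 days (section 6.2). The total can exceed 12 months.

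**2. Nearest existing criteria (section 6.6).** A bypassed upper airway is one narrow surgical state. Nasal deformity excludes a deformity present now, not one corrected after the diagnostic study. Neither closes the gap.

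**3. Model.** Let b be the diagnostic AHI and d the fraction by which untreated AHI has since fallen. The value of d is an assumption. With no device effect and no night-to-night noise, PSG AHI = b(1 − d) and measured change = d × b.

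**4. PSG 1 rule.** Section 6.2 keeps a subject only if AHI falls below 10 or by at least 50% from the diagnostic value. I read the former condition as AHI < 10.

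- d = 0.30: the reduction is under 50%, so b × 0.70 < 10 is needed, i.e. b < 10/0.70 = 14.3. The largest change is 14.3 × 0.30 = 4.3. Spread over 10 completers: 4.3/10 = 0.43 events/h per affected subject.
- d = 0.50: every b from 5 to 30 passes. At b = 20 the change is 10, adding 10/10 = 1.0 events/h; at b = 30 it is 15, adding 1.5.

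**5. If the device works.** Take a proportional device effect e. Excess change due to drift = b × d × (1 − e). With b = 20, d = 0.30, e = 0.50: AHI goes 20 → 14 → 7, the subject passes, and the excess is 20 × 0.30 × 0.50 = 3, or 0.3 events/h on the mean of 10.

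**6. Direction among completers.** Take b uniform on 5 to 30 (assumed) and no device effect. A 30% fall passes PSG 1 for b < 14.3: (14.3 − 5)/25 = 37%. A 30% rise passes only for b < 10/1.30 = 7.7: (7.7 − 5)/25 = 11%. The rule therefore retains falls more often than rises.

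**7. Share of completers affected.** Same assumptions, with 20% of enrolled subjects affected. Unaffected subjects pass when b < 10: 5/25 = 20%.

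- 50% fall: share = 0.20 × 1 / (0.20 × 1 + 0.80 × 0.20) = 0.20/0.36 = 56%. Mean b is 17.5, so the completers' mean apparent change is 0.556 × 0.50 × 17.5 = 4.9 events/h.
- 30% fall: share = 0.20 × 0.371 / (0.20 × 0.371 + 0.16) = 0.074/0.234 = 32%. Mean b among those passing is (5 + 14.3)/2 = 9.6, so the mean change is 0.317 × 0.30 × 9.6 = 0.9 events/h.

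Simulation with night-to-night noise (log-scale SD 0.2 and 0.3) gave completers' means of 3.5 and 3.1 for the 50% case and 0.9 and 0.8 for the 30% case, against −0.2 and −0.4 with no drift.

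**The case against.** **The sponsor has a fair reply.** Baseline age is capped at 12 months and the 3% hypopnea criterion is fixed. Medical history, BMI and medications are collected, so interim surgery or treatment may well be noted. Section 4.1 says the design and endpoints were discussed with the FDA, and section 8.1 says that 10 subjects were accepted. Drift can also work against the device, as with weight gain.

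Much of this stands. It would be wrong to say that a comparison with the time of diagnosis is impossible; the accurate statement is that none is planned and nothing acts on what is recorded. The FDA statements do not show that interim treatment or weight change was considered.

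**Three stronger readings are tempting but unsupported.**

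- A reader might infer that CPAP non-adherent patients are especially likely to have sought other treatment or lost weight, so that AHI mostly drifts down. The documents say nothing on this, and section 6.5 also admits current CPAP users. The lean toward the device comes from the PSG 1 rule, not from presumed patient behavior.
- A reader might take baseline 20 with a 30% fall and no device effect, and count 6 events, or 0.6 events/h on the mean of 10. That subject has AHI 14 at PSG 1, meets neither condition and is terminated, so without noise the contribution is zero.
- A reader might point to drift alone producing an AHI below 10, for example 13 × 0.75 = 9.75. This is true but secondary: the primary endpoint is the change, and diagnostic values from 5 to below 10 are eligible and below that threshold with no drift at all.

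**Conclusion.** The concern holds as a gap in eligibility and planned checking. A subject whose untreated AHI changed after the diagnostic study can enter, and the plan would attribute that change to the Bongo. In the no-effect, no-noise illustration, one affected completer adds at most 0.43 events/h to the mean of 10 after a 30% fall, and 1.0 after a 50% fall from 20.

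These sizes rest on assumed drift, and the group-level figures also on an assumed baseline distribution and an assumed 20% affected. The documents support none of these values, so actual bias may be negligible. The lean toward the device depends on the PSG 1 rule removing some subjects; if nearly everyone passed, rises and falls would both remain. This is a minor recommendation and does not call for a different endpoint, sample size or visit schedule.

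**What to change.** 1. Add to section 6.6: *Since the diagnostic PSG: upper airway, nasal or bariatric surgery, or start of an oral appliance or other non-CPAP OSA treatment.* Check it from the medical history already taken at screening.
2. Where available, copy weight at the diagnostic PSG to the CRF. State in section 8, before data are seen, the weight difference that triggers a flag, and report the mean AHI change with and without flagged subjects.
3. List months from diagnostic PSG to PSG 2 for each subject.

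**Cost.** One criterion, a few CRF fields and one extra line in the results. Expect a few more screen failures within the cap of 20 enrolled. Subjects come from the sleep center's own rolls (section 5.2), but the protocol does not say that diagnostic weight is on file, so it may be missing for some; report how many.

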5.1 Study Outline and Design

This study is a prospective, non-randomized, open label, single-center clinical study for the BONGO NASAL EPAP device for the treatment of obstructive sleep apnea.

Subjects will have the following study schedule:

1. Screening
2. In-lab PSG 1 with the Bongo
3. 2 week at home use of the Bongo
4. In-lab PSG 2 with the Bongo
5. Study termination visit (may be completed the morning following PSG 2)

5.2 Subject Recruitment and Screening

Subjects will be recruited from existing patient rolls within the participating sleep center. The patient rolls provide the first line of screening for inclusion criteria and exclusion criteria. Phone screening will be conducted to further assess meeting the inclusion criteria and exclusion criteria (e.g. do they use a full face mask or are they mouth breathers). Additional screening will be conducted during the screening visit. Data obtained from screening will not be retained and the site will follow their standard procedures for destroying the data.

